#### Experimental

#### **Screening Tests**

a) Telephone Screening Potential participants will be asked screening questions over the phone. Only those without exclusion criteria will be scheduled for an in-person screening visit.

b) History & physical examination will be performed by [name] (board-certified Internist and Geriatrician) to document medical history and physical exam findings according to key inclusion/exclusion criteria (see Human Subjects). The history & physical examination will also include screening questions for cognition, quality of life, and depression. Human studies will be conducted in the Bartter Research Unit (BRU) of the ALMVAH and at the MARC on the 3rd Floor; however, the Visits 2, 8 and 14 which include the Insulin Clamp and Muscle Biopsy will continue to be done at the ALMVAH BRU. Waist circumference using the World Health Organization protocol will also be measured as part of the history & physical examination.

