a) Activity monitoring. An activity monitor (Actigraph, LLC) will be used to monitor physical activity over a 10 day period. The monitor will be mailed to the participant approximately 2 weeks prior to a scheduled visit. He or she will place the monitor on the wrist as he or she would a watch, and wear until returning to the next visit or we will provide a postage paid envelope for the participant to mail back to the study team. We will retrieve the monitor at this time. This measurement will be taken prior to randomization and then at 2 time points following randomization (see table of study visits and procedures below).

b) Body composition. Whole body DEXA is performed to measure lean and fat body mass (lean mass values are used to adjust insulin sensitivity values) and to examine the effect of the interventions on body composition.

c) Insulin clamp: Insulin sensitivity will be measured after an overnight fast using a 130-min euglycemic hyperinsulinemic (40mU.m^-2) clamp with tritiated glucose as described (DeFronzo, 1979). Indirect calorimetry is performed during the 45 min prior the clamp and 30 min before the end of the insulin clamp to measure fat and carbohydrate oxidation and oxidative and non-oxidative glucose disposal. This procedure will not be performed if subject has donated blood within the last 2 months; subject does not have normal electrolytes (potassium  $\geq 3.3$  mmol/L); there is difficulty obtaining IV access; if the patient has had high exposure to radiation in the last year from general medical care ( $>50$  millisieverts) (Hruska & O'Connor, 2015); or for any other concern as determined by the PI.

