9. **Radiation exposure.** Subjects will be exposed to a small amount of radiation during the insulin clamp and dual-energy x-ray absorptiometry (DEXA) exam (36.48 mrem), which is approximately 17% of the average amount of natural environmental radiation exposure (620 mrem dose) that each member of the general public receives per year. Tritiated glucose is given during the insulin clamp studies. The radiation exposure from tritiated glucose is well within guidelines (Shreve et al., 1958; U.S. Department of Commerce National Bureau of Standards Handbook 69, 1969). The cumulative radiation exposure is well within the dose range (1,000 mCi) approved by the University of Texas Health Science Center Radiation Safety Committee. At these low exposures, risk is minimal. If a participant has had exposure to radiation due to medical tests or treatments and the estimated total exposure within one year is expected to be  $> 1,000$  mCi, the insulin clamp and/or DEXA exam will not be performed at the discretion and estimation of the PI.

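### The radiation limit for withholding the clamp and/or DEXA is stated in a unit of activity and not linked to the separate 50 mSv clamp limit, and the stated 17% of background does not follow from the figures beside it

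*Combined protocol and SAP*

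**What the plan says.** Radiation limits appear in two places in Item 6 of the combined protocol and SAP.

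- **Study Procedures, c) Insulin clamp.** The clamp is not performed if the participant has had "high exposure to radiation in the last year from general medical care", set at more than 50 millisieverts. The list of reasons ends with any other concern of the PI. The entry above it, b) Body composition, gives no radiation limit for DEXA.
- **Potential risks, 9. Radiation exposure.** The committee-approved range is given as "The cumulative radiation exposure is well within the dose range (1,000 mCi"). The last sentence concerns participants exposed through medical tests or treatments. If their "estimated total exposure within one year is expected to be" above 1,000 mCi, "the insulin clamp and/or DEXA exam will not be performed at the discretion and estimation of the PI".

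The risk section also gives the study's own exposure: "dual-energy x-ray absorptiometry (DEXA) exam (36.48 mrem"), "which is approximately 17% of the average amount of natural environmental radiation exposure (620 mrem dose"). The 620 mrem is described as an annual figure: "620 mrem dose) that each member of the general public receives per year".

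Screening Tests, b), fixes the scheduled clamp sessions: "Visits 2, 8 and 14 which include the Insulin Clamp and Muscle Biopsy". The note under the visit table places DEXA at the same time points, with Visits 7 and 13 as alternatives to 8 and 14. Study Procedures, k) Management of conversions, adds a clamp and DEXA at conversion to diabetes. These stand in for the 12- or 24-month set only if done within one month of it.

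**The concern.** The risk section contains a decision limit and a safety figure, and neither works as written.

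The limit is in millicuries. That unit describes how much radioactive material is present or administered. Exposure from scans or treatments is recorded as dose, in mrem or mSv, and no fixed factor converts one to the other. A PI who adds up a participant's medical exposure cannot compare the total with 1,000 mCi. For the clamp there is a second limit in a usable unit, but the protocol does not say how the two relate. For DEXA there is no other limit.

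The safety figure compares the study's exposure with natural background, and its percentage disagrees with the two numbers in the same sentence.

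What is at stake is mainly participant-safety text in a trial of adults aged 65 and over. There is a smaller effect on the data. The clamp is an Aim 2 measure, and DEXA provides both body composition, a secondary outcome, and the lean mass used to adjust insulin sensitivity. An unclear rule for withholding these procedures therefore makes it unclear who contributes those measurements.

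**Working it through.** **Percentage of background**

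Inputs, all from Item 6: 36.48 mrem (clamp and DEXA, basis not stated), 620 mrem per year (background), about 17% (stated share), three scheduled sessions.

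Formula: share = number of sessions × 36.48 / background × 100.

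The stated figure, taken as written:

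- 36.48 / 620 = 0.0588, or 5.9%. The stated 17% is not reproduced.
- Working backwards, 17% of 620 mrem is 105.4 mrem. For 36.48 mrem to be 17%, background would have to be 36.48 / 0.17 = about 215 mrem.

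Other bases that might have been intended:

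| Sessions | Total, mrem | Share of one year (620) | Share of two years (1,240) |
|---|---|---|---|
| 1 | 36.48 | 5.88% | 2.94% |
| 2 | 72.96 | 11.77% | 5.88% |
| 3 (as scheduled) | 109.44 | 17.65% | 8.83% |
| 4 (with a conversion repeat) | 145.92 | 23.54% | 11.77% |

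Only three sessions against one year of background come near 17%, and 17.65% would round to 18%. That reading needs 36.48 mrem to be a per-session dose, which the sentence does not say. It also sets sessions spread over two years against a single year of background.

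**The two limits side by side**

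| | Study Procedures, c) | Potential risks, 9 |
|---|---|---|
| Value | more than 50 mSv | more than 1,000 mCi |
| Quantity measured by the unit | dose | activity |
| Exposure counted | past year, general medical care | estimated total expected within one year, in participants with medical exposure |
| Procedures | clamp | clamp and/or DEXA |
| PI judgement | other concerns of the PI | discretion and estimation of the PI |
| Refers to the other text | no | no |

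In common units, 50 mSv × 100 mrem per mSv = 5,000 mrem. The other limit is 1,000 mCi = 37 GBq, which is an activity and has no equivalent in mSv without further information. The limits cannot be ranked, and the text does not show whether they are two statements of one rule or two rules.

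**The case against.** Several points can fairly be made in defence of the text.

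- **The clamp has a usable limit.** The 50 mSv criterion is in a dose unit and sits in the clamp procedure itself. This stands. It would be too strong to say that staff have no workable rule for the clamp. It does not help DEXA.
- **The two limits may be separate conditions.** One looks back at clinical exposure and covers the clamp. The other can be read as a projected total and covers both procedures. This also stands, so the documents do not prove a contradiction between two values of one limit. The gap is that the text does not say which is meant.
- **The PI has discretion in both places.** True, but discretion does not turn an activity into a dose.
- **Millicuries are natural for a tracer.** The first use of 1,000 mCi follows the sentences on tritiated glucose and could be an approved activity, although the text calls it a dose range. The second use, for exposure from medical tests or treatments, cannot be explained in this way.
- **The 17% is close to the three-session total.** It is, and this may be its origin.

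A reader might go further and infer a fivefold gap between the limits, with different participants losing the clamp depending on the section followed. That requires 1,000 mCi to mean 1,000 mrem (10 mSv against 50 mSv). Nothing in the documents supports that substitution, and taken literally the millicurie limit decides no one's case. A reader might also infer that exposure is understated threefold. That is conditional: if 36.48 mrem is per session, the printed 17% already conveys roughly the scheduled total, and if 36.48 mrem is the total, 17% overstates it.

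**Conclusion.** The point holds in three parts.

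1. The limit in the risk section is in a unit that cannot measure medical exposure. It is unusable as written, and it is the only radiation limit stated for DEXA.
2. Its relation to the 50 mSv clamp limit is not stated. Whether these are one rule or two is open, and the documents give no basis for expressing the difference as a ratio.
3. On the printed figures the study exposure is 5.9% of one year's background, not 17%. The 17.65% for three sessions depends on the assumption that 36.48 mrem is per session.

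The stated exposure is small on every reading: even four sessions total 145.92 mrem, below the 620 mrem given for one year of background. The documents do not give the number of participants who might have a procedure withheld on radiation grounds, so the effect on clamp and DEXA data cannot be sized. Aim 2 also has an OGTT-based insulin sensitivity measure, the Matsuda index, which does not depend on these limits. Sample size, power and the Aim 1 frailty outcome are not affected. This is a safety-text correction that should be made, and not a flaw in the design.

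**What to change.** - Reconcile Study Procedures, c) Insulin clamp with Potential risks, 9. Radiation exposure. State whether they are one rule or two, which procedures each covers, and whether each counts past exposure or a projected total.
- Express the limit in the risk section in a dose unit, with the value confirmed by the sponsor and the radiation safety committee. Which value applies, and whether the clamp and DEXA share a limit, is for them to decide.
- If the first 1,000 mCi was meant as an approved tracer activity, say so and keep it apart from any dose limit.
- State whether 36.48 mrem is per session or in total, and over what period. Give the percentage that follows: 5.9% for 36.48 mrem against one year, or 17.65% for three sessions against one year, with the two-year span noted. Mention the possible extra session at diabetes conversion.
- Item 7 says that risks are described in the consent document. If the 17% or the millicurie limit is repeated there, correct it in the same way.

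The cost is a wording amendment and one check with the radiation safety committee. No analysis or sample-size work is needed.

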#### Data Analysis Plan:

### STATISTICAL METHODS & POWER CALCULATIONS

**Overview.** In all analyses for Aim 1 and Aim 2, primary inference will be drawn based on intention to treat (ITT) analyses. Average complier effect (ACE) will be used to inform the metformin effect under full compliance to treatment assignments (Angrist et al, 1996). Per protocol analyses will be used to inform the metformin effect among completers. All analyses will be carried out unadjusted and with adjustment for covariates (Table 7) and covariate interactions with treatment and time. Corrections for multiple comparisons will be applied as appropriate.

The impact of metformin treatment on the progression of frailty status (non-frail, pre-frail, frail) over time will be assessed with a repeated measures mixed effects multinomial logistic model that models the log-odds of adjacent frailty statuses in terms of an indicator of metformin use, time, and the metformin use by time interaction. The possibility of non-linear trends of the log-odds of frailty statuses will be assessed by including an additional time factor (e.g., time squared) and its interaction with metformin use. The best fitting model will be used for inference. Secondary outcomes including gait speed, 6 minute walk, SPPB, frailty index constructed from the research data collected according to the Rockwood index (Searle et al., 2008; Rockwood et al., 2007), and body composition will similarly assessed. Under the linear trend model, the beneficial impact of metformin will be revealed by a significant time by treatment interaction associated with the log-odds of frailty status progression, indicating that the rate of increase in the likelihood of frailty progression over time is reduced in the metformin arm relative to the placebo arm. Under the non-linear trend model, the impact of metformin will be revealed by a significant reduction in the log-odds of frailty status progression in the metformin arm versus placebo at certain time points during the follow-up. SAS proc **nlmixed** will be used in the mixed effects model analyses. Proc **nlmixed** is preferred over other mixed effects modeling procedures such as GEE because it is valid under missing at random (MAR) assumption, accommodates linear and non-linear modelling, and uses maximum likelihood estimation.

Table 7. Covariates included in statistical analyses

Categories of covariates	Baseline	Time Varying
Demographics (age, sex)	X	
BMI (obesity), sarcopenia	X	X
Lipids, blood pressure	X	X
Fasting glucose, HbA1c, Insulin Sensitivity from OGTT (Matsuda) and Insulin Clamp	X	X
Inflammation (systemic & muscle), Insulin Signaling (muscle)	X	X
Diabetes conversion		X
Pioglitazone use		X

Of secondary interest, a per protocol analysis will be carried out with restriction to patients who follow the protocol throughout the study, and where those who drop out, violate the protocol or change treatments are excluded. Separately, those who change treatments will be summarized and described. To account for any treatment change, we will also consider principal stratification analysis (which requires categorization of patients based on treatment change patterns) and marginal structural modeling (which obtains the overall metformin effect accounting for treatment change, and time-varying covariates (e.g., diabetes status), and outcomes (e.g. frailty, physical function) history.

Metformin dose will be handled in the statistical analysis by conducting dose-response analysis among metformin users. Several options of metformin dose/exposure variables will be considered in separate analyses: average daily dose, clinical meaningful threshold for average daily dose, total days of supply, and clinical meaningful threshold for total days of supply. Should there be any discrepancy among these dose-response analyses, we will reconcile these results for the final interpretation.

**3.D.3. Power Calculation for Aim 1.** With 60 completers per arm, this study will achieve a power of 86% to detect an overall odds ratio of 0.20 for a one ordinal category increase in the frailty score in metformin versus placebo based on SAS **proc nlmixed** analyses of 1000 simulated databases with 6 repeated measures per subject, all subjects at frailty score 0 or 1 at baseline, an increasing random pattern in the placebo group, a pattern of lower frailty scores with increasing time on study in the treated group, and 10% of subjects in each arm remaining at baseline levels throughout all subsequent visits, two-sided testing, and a significance level of 5%.  At visits 1 through 6 Placebo subjects were assigned a 56% chance of increasing by one level, 22% staying the same, and 22% decreasing by one frailty level, and Treated subjects were assigned a 33% chance of increasing by one level, a 33% chance of staying the same, and a 33% chance of decreasing by one frailty level relative to the previous visit. With these parameter values, at baseline 50% of subjects were at frailty level 0 and 50% at level 1 in each arm and at visit 6 the distributions for Placebo were 0: 25%, 1: 22%, 2: 20%, 3: 18%, 4: 11%, 5: 4% on the average across the 1000 simulations. Distributions for Treated were 0: 50%, 1: 24%, 2: 14%, 3: 11%, 4: 0%, 5: 0% on the average across the 1000 simulations.

**3.D.4. Aim 2.** To address the question as to whether an anti-frailty effect of metformin is mediated by its insulin sensitizing and anti-inflammation effects, we will employ the unified mediation analysis framework by Vanderweele. Insulin sensitivity (Matsuda index derived from the OGTT) will be measured at baseline, 6, 12, 18 and 24 months, and 8 biomarkers of systemic inflammation (IL-6, CRP, TNFa, IL-1RA, TNFs R1 and 2, fibrinogen, and transferrin), insulin sensitivity (clamp) and multiple biomarkers of muscle inflammation and insulin signaling (NF $\kappa$ B and MAPK signaling, and mRNA levels of inflammatory cytokines) will be measured at baseline, 12 months, and 24 months. First, we will conduct separate repeated measures mixed effects linear model analyses to assess the effect of metformin treatment on each insulin sensitivity and inflammation measure. In each of these analyses, the outcome (or its normal transformation) will be modelled in terms of an indicator of metformin treatment, time, the treatment by time interaction, and covariates. The coefficient associated with the treatment by time interaction will inform the effect of metformin on the temporal change of each biomarker. We will then conduct repeated measures mixed effects multinomial logistic model to assess whether the odds of an increase in the frailty score is associated with the change in insulin sensitivity from baseline to 24 months ( $\Delta$ IS), and change in inflammation from baseline to 24 months ( $\Delta$ I) by modelling the log-odds of frailty worsening in terms of metformin treatment, time,  $\Delta$ IS,  $\Delta$ I, (metformin) treatment $\times$ time, and covariates. The treatment $\times$ time $\times$  $\Delta$ IS and treatment $\times$ time $\times$  $\Delta$ I interactions will be explored to assess whether metformin attenuates the effect of  $\Delta$ IS and  $\Delta$ I: this effect will be revealed by a significant coefficient associated with treatment $\times$ time $\times$  $\Delta$ IS or treatment $\times$ time $\times$  $\Delta$ I. If some  $\Delta$ IS and  $\Delta$ I measures are collinear, then we will model the odds of frailty worsening in terms of  $\Delta$ IS and  $\Delta$ I separately. All of these analyses will be initially carried out for a pair of an inflammation biomarker and an insulin sensitivity marker separately. Aim 2 will be verified in principle if (i) metformin is associated with significant increase in  $\Delta$ IS and decrease in  $\Delta$ I; and (ii) frailty worsening is

associated with significant decrease in  $\Delta IS$  and increase in  $\Delta I$ ; and (iii) the indirect effects of metformin (mediated by  $\Delta I$  and  $\Delta IS$ ) calculated based on Vanderweele are significant.

**3.D.5. Power Calculation for Aim 2. Inflammation.** A 3 month clinical trial of insulin sensitizers versus placebo in patients with impaired glucose fasting glucose or diabetes found decreased TNF $\alpha$  in treated patients (effect size =1.5) . Assuming the same or larger decrease in TNF $\alpha$ , 60 completers in each group, 6 repeated measures, autocorrelation 0.5, and overall type 1 error of 0.05, we expect to have power  $\geq 95\%$  to detect a group difference with regard to mean TNF $\alpha$  and power  $\geq 95\%$  power to detect an increase in TNF $\alpha$  and frailty worsening in the combined cohort [PASS Version 11, NCSS Kaysville UT 2011]. **Insulin sensitivity.** The Diabetes Prevention Program demonstrated improved fasting glucose in metformin treated adults (decrease of 4.1 mg/dL) with pre-diabetes and increased fasting glucose (by 0.4 mg/dL) in placebo group . Assuming the same treatment effect on fasting glucose in this study, and n=60 completers per arm, this study will attain a power of 80% for testing the null hypotheses of no treatment effect, two sided testing, 6 repeated measures, and an autocorrelation of 0.5 [PASS Version 11, NCSS Kaysville UT 2011].

**3.D.6. Time to major adverse event.** The relation between treatment and time to major adverse outcome will be studied with and without adjustment for covariates and will be described with Kaplan-Meier curves. An adverse outcome will be defined as a) 2 point increase in the frailty score, or b) fall resulting in bone fracture or other serious injury, c) admission to a nursing home or skilled care facility, or d) death. The time to adverse outcome will be defined as the time to first occurrence of any of a), b), c) or d) and will otherwise be considered censored at loss to follow-up or end of study. Without adjustment, treatment groups will be contrasted on time to major adverse outcome with a logrank test and the treatment-specific accumulated incidence of adverse outcome will be described with Kaplan-Meier curves and 95% confidence bands. An adjusted contrast of treatment groups will be carried out with a Cox proportional hazards model in terms of treatment group, age, ethnicity, gender, and baseline values of frailty score. OGTT and inflammatory biomarkers will be entered as time-dependent covariates. Logrank testing, Kaplan-Meier estimates of survival distributions, and covariate adjusted Cox modelling of relative risks accommodate non-informative right censored survival data.

**3.D.7. Missing Data.** Limited missingness in outcomes and associated covariates is possible due to loss to follow-up. Missing covariates without loss to follow-up may occur due to missed appointments and intercurrent illness. In the primary analyses, model estimates will be derived based on the likelihood of observed data, an approach that gives consistent estimates under the MAR assumption: “missingness” depending upon the observed data but not the unobserved. To further address the possibility of missing data under the MAR assumption, we will conduct all analyses without and with multiple imputation using SAS proc mianalyze and its companion procedure proc mi. The mianalyze procedure combines the results of the analyses of imputations and generates valid statistical inferences and MI creates multiply imputed data sets for incomplete multivariate data.

**3.D.8. Randomization.** Participants will be randomized to metformin or placebo in a balanced design.

3.3.9. Blinding. This study is double blinded. Only the study pharmacist has knowledge of the medication each participant is taking. As per the requirement by the NIA-appointed DSMB, one study statistician has been and will remain unblinded. The unblinded study statistician will prepare DSMB reports as per the guidelines provided from the National Institute on Aging (<https://www.nia.nih.gov/research/dgcg/clinical-research-study-investigators-toolbox/data-and-safety-monitoring>). Any unblinded report will be reviewed during a closed DSMB session with only the unblinded statistician present and without any study investigators present.

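### The adjusted Cox contrast, and the adjusted Aim 1 model if Table 7 is applied as written, condition on post-randomisation variables, and no sentence names the unadjusted ITT analysis as primary

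*Combined protocol and SAP*

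**What the plan says.** The Overview bases primary inference for both aims on ITT and then states: "All analyses will be carried out unadjusted and with adjustment for covariates (Table 7) and covariate interactions with treatment and time". It does not rank the two versions.

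Table 7 has a baseline and a time-varying column. The row "Fasting glucose, HbA1c, Insulin Sensitivity from OGTT (Matsuda) and Insulin Clamp" is ticked in both, as are the rows for BMI and sarcopenia, lipids and blood pressure, and inflammation with insulin signalling. Diabetes conversion and pioglitazone use are ticked only as time-varying.

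The Aim 1 model is written without covariates: "in terms of an indicator of metformin use, time, and the metformin use by time interaction". Section 3.D.3 lists none either when it says "this study will achieve a power of 86% to detect an overall odds ratio of 0.20".

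Section 3.D.6 plans an unadjusted logrank test and an adjusted Cox model with treatment, age, ethnicity, gender and baseline frailty score, and adds: "OGTT and inflammatory biomarkers will be entered as time-dependent covariates".

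In Section 3.D.4 the first-step biomarker outcome "will be modelled in terms of an indicator of metformin treatment, time, the treatment by time interaction, and covariates"; the covariates are not listed. The same section asks "whether an anti-frailty effect of metformin is mediated by its insulin sensitizing and anti-inflammation effects".

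To account for treatment change, the plan will also consider "marginal structural modeling (which obtains the overall metformin effect accounting for treatment change, and time-varying covariates (e.g., diabetes status" and outcome history.

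**The concern.** A randomised comparison estimates the total effect of assignment when it conditions on nothing, or only on quantities fixed before randomisation. Conditioning on a value that treatment may have altered removes whatever part of the effect runs through it. It also opens the comparison to any unmeasured cause shared by that value and frailty. The result is an effect conditional on post-randomisation variables, under assumptions that randomisation does not secure.

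The plan would report two ITT versions of each result, one of which does not estimate the ITT effect, with no stated primary. A weaker adjusted result could be read as no independent effect of metformin, and a stronger one as the metformin effect. Either may reflect only the conditioning.

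**Working it through.** **1. Covariate timing against the stated mechanism.**

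| Variable | Where it enters | Role the protocol gives it |
|---|---|---|
| Insulin sensitivity, glycaemia | Table 7, time-varying; OGTT in the 3.D.6 Cox model | Route of metformin's effect (Item 4; Research Design, Aim 2, mechanism 1; 3.D.4) |
| Inflammation | Table 7, time-varying; biomarkers in the Cox model | Route of metformin's effect (Item 4; Aim 2, mechanism 2; 3.D.4) |
| Diabetes conversion | Table 7, time-varying only | Part of mechanism 1; once confirmed, allocation is unblinded and placebo subjects start metformin (Item 6, Management of conversions) |
| Pioglitazone use | Table 7, time-varying only | Follows conversion and HbA1c, so is necessarily post-randomisation |
| BMI, sarcopenia | Table 7, time-varying | Not named as a pathway, but weight enters the frailty definition after baseline |

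**2. Is a primary version named?** The ITT sentence does not say adjusted or unadjusted. The Aim 1 formula and the power calculation point to unadjusted. The reference to primary analyses in 3.D.7 concerns likelihood estimation under MAR and chooses neither. The formula's treatment term is metformin use, which can differ from the randomised arm once placebo converters start metformin.

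**3. How far a coefficient can move.** In a linear model,

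adjusted coefficient = unadjusted coefficient − (treatment shift in marker) × (marker's slope on outcome),

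whether or not the marker causes the outcome. The documents give partial inputs:

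- Slopes (Background, Role of Inflammation in Frailty; cross-sectional, frail versus non-frail, normal approximation). IL-6: (4.4 − 2.8)/√((2.9² + 1.6²)/2) = 0.68 log-odds per SD. CRP: (5.5 − 2.7)/√((9.8² + 4.0²)/2) = 0.37. Halved for two status steps: 0.34 and 0.19.
- Shifts (3.D.5). TNF-α: 1.5 SD. Fasting glucose: a 4.1 + 0.4 = 4.5 mg/dL difference at 80% power, 60 per arm, 6 measures and autocorrelation 0.5 implies 2.80 × √((2/60) × v). With v = 0.583 (compound symmetry) this is 0.39 SD; with v = 0.391 (AR(1)), 0.32 SD.
- Product: 0.32 × 0.19 = 0.06 to 1.5 × 0.34 = 0.51 log-odds, a factor of 1.06 to 1.67 on the odds ratio.

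These products pair one marker's shift with another marker's slope; the documents give no marker with both. The sign follows the slope. BMI shows that it need not be one-way: frailty went with higher BMI at baseline in the earlier cohort (Table 2), yet losing at least 5% of baseline weight counts toward frailty after baseline. No metformin shift in BMI is given.

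**4. What conditioning on the pathway could do.** Take the stated 86% as given. It implies a standardised effect of 1.96 + 1.08 = 3.04. If a share m of the log odds ratio runs through the adjusted variables and the standard error is unchanged, OR = 0.20^(1−m) and power = Φ((1−m) × 3.04 − 1.96) plus the opposite tail.

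| m (assumed) | OR | Power |
|---|---|---|
| 0 | 0.20 | 86% |
| 0.25 | 0.30 | 63% |
| 0.50 | 0.45 | 33% |
| 0.75 | 0.67 | 12% |
| 1 | 1.00 | 5% |

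**5. Mediator-outcome confounding.** In a linear simulation (60 per arm, 4,000 runs per setting), the ratio of adjusted to unadjusted coefficient was 1.00, 0.50 and 0.00 for m = 0, 0.5 and 1 with no shared cause. With an assumed unmeasured shared cause (loading 0.6) it was 0.36, −0.14 and −0.65. The unadjusted coefficient stayed at the total effect throughout.

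**6. Why no error rate is offered as the size.** With no true effect, slope 0.34 and a 1.5 SD shift growing to month 24, two simulations of the adjusted Aim 1 model gave 13.6% false significance (placebo worsening set to 56%) and 36.5% (about 70%, with its own marker construction). At 0.39 SD they gave 5.0% and 7.5%. The answer depends on calibration that the documents do not settle.

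**The case against.** The strongest reply is that the total effect is already planned and is the model written out. Every analysis is run unadjusted, the Aim 1 success criterion is attached to a formula with no covariates, the power calculation lists none, and 3.D.6 includes the unadjusted logrank test. This stands: a reader might infer that the trial will not report a valid ITT result, and the documents do not support that.

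Table 7 also serves both aims and does not say that each time-varying value enters each treatment model; mediation and marginal structural models are legitimate uses. This is fair, but the Overview applies Table 7 to all analyses without exception, and 3.D.6 is explicit. Marginal structural modelling is only to be considered and would not change what the adjusted Cox or Aim 1 coefficient means.

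A reader might also infer that the first-step Aim 2 models adjust for mediators. Section 3.D.4 does not say so. Reading in Table 7's time-varying column is an inference from the Overview, and taken literally it would include Aim 2's own outcomes among the covariates. What is shown is an unspecified list. The later mediation step conditions on changes in insulin sensitivity and inflammation by design and is not at issue.

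Finally, a reader might infer that adjustment must weaken the effect. If the mechanism holds, that is the likelier direction, but neither sign nor size follows from the documents.

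**Conclusion.** The point holds for the adjusted Cox treatment contrast on its explicit wording, and for the adjusted Aim 1 model if Table 7 is applied as written. Neither coefficient is the total ITT effect; both condition on post-randomisation values and are open to mediator-outcome confounding. The unadjusted Aim 1 model and the logrank test are unaffected, and the missing statement of which analysis is primary is a real gap. For the first-step Aim 2 models the finding is only that the covariates are unspecified.

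This should be fixed, but it is a risk to interpretation rather than a loss of the main result. Confidence is high for the Cox terms and the missing label, and lower for Aim 2. The calculated magnitudes are illustrative: the mediated share, the shared cause and the cross-marker pairings are assumptions.

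**What to change.** Change the SAP wording as follows.

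- **(a)** Name one primary Aim 1 ITT analysis by randomised arm, either unadjusted or adjusted for prespecified baseline covariates only.
- **(b)** Remove the time-dependent OGTT and biomarker terms from the adjusted Cox treatment contrast in 3.D.6, and keep its baseline terms.
- **(c)** State that the adjusted treatment-effect models for Aim 1 and the first-step Aim 2 models draw only on Table 7's baseline column. Diabetes conversion and pioglitazone use have no baseline entry and so drop out of these models.
- **(d)** Label any treatment model with time-varying covariates, including the mediation and marginal structural models, as mechanistic or exploratory, and state that it does not estimate the ITT effect.

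The cost is wording only. The baseline values are already collected, and no visit, procedure or unadjusted analysis changes.
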